Title: Parent/Nurse Controlled Analgesia in the Neonatal Intensive Care Unit

NCT Number: NCT01823497

Document Date Feb 7, 2013 (Date of IRB approval)

Methods

This single-center, prospective, RCT was approved by the hospital Institutional Review Board, and was registered at www.clinicaltrials.gov (ID: NCT01823497) by the principal investigator prior to study enrollment.

Setting

This study took place in the NICU at Children's Hospital of Wisconsin (CHW), with data collected between April 2013 and April 2015. At the time of the study, the unit consisted of a 43 bed intensive care unit and a 16 bed step-down unit with approximately 600 admissions per year.

Procedure

Potential participants were identified from the surgery schedule and the surgical team's work list that included any infant with a planned surgery. Initially, the study team also made contact with the mothers of potential participants in the hospital's Fetal Concerns Clinic. However, this recruitment method was unsuccessful, and was therefore discontinued.

Inclusion criteria: Infants 1) born no earlier than 34 weeks post menstrual age and having a corrected age no greater than 44 weeks at the time of enrollment, 2) having a birth or current weight of at least 2 kg, 3) undergoing an abdominal or thoracic surgical procedure conducted by the pediatric general and thoracic surgery team, and 4) expected to require opioids for at least 24 hours after the surgical procedure based on the opinion of the surgeon. Additionally, at least one parent was able to read and speak English. As recruitment proved more difficult than anticipated, the protocol was amended to remove the upper age limit, but the requirement of being cared for in the NICU remained.

Exclusion criteria: Infants 1) requiring vasopressors, 2) with significant prior opioid exposure (defined as > 2 days of continual exposure before surgery, or > 3 doses over the 5 days prior to the surgery), and 3) who were expected to be chemically paralyzed after surgery.

Design

This study utilized an unblinded design. Parents were approached prior to surgery. After informed consent was obtained, infants were randomized to 1 of 2 arms: either the morphine PNCA with a basal infusion (PNCA) group, or the morphine COI group. Randomization was stratified by gender and surgical location (thoracic, upper or lower abdomen) in blocks of 4. The randomization scheme was created by a statistician on the research team using Windows version 6.0 of “rand.exe” (<http://block-stratified-randomization.software.informer.com/>). The clinical research coordinator used the scheme to assign participants to groups.

Protocol Details

Morphine was administered using PNCA for Group 1 and COI for Group 2. Conditions were designed to replicate current pain management procedures in our NICU. For the PNCA group, orders were entered by a member of the Acute Pain Service (APS) or the patient's anesthesiologist. Using a 250 mcg/mL solution, PNCAs were ordered as morphine 0.010-0.0125 mg/kg button dose, 8 min lockout, 0.010-0.0125 mg/kg/hr basal rate, and 0.060 mg/kg/hour total maximum. Doses were rounded to the nearest microgram. Parents were instructed on signs of pain, to only push the PNCA button when the child was awake and in pain, never to push the PNCA button when the child was asleep, and to notify their nurse if they felt their child's pain was not well controlled. For the COI group, morphine was ordered at 0.030 mg/kg/hr with a 0.030 mg/kg/hr nurse bolus available each hour to a maximum of 0.060 mg/kg/hr total. Parents were instructed on signs of pain and to notify their nurse if their child's pain was not well

controlled. The post-surgical opioid delivery system was initiated upon return to the NICU. Based on our current practice, PNCA patients were managed by the APS and COI patients were managed by the neonatology team. COI patients were checked on daily by the APS, but opioid adjustments were made only by the neonatology team. Monitoring of all patients was consistent with current practice. Patients had continuous pulse oximetry and cardiopulmonary monitoring. Pain and sedation scores (Hoffman, Nowakowski, Troshynski, Berens, & Weisman, 2002) were recorded at least every 2 hours for the first 24 hours, with a minimum of every 4 hours thereafter. To calculate total opioid consumption, PNCA doses (PNCA group) and morphine boluses (COI group) were documented hourly.

Enrolled patients who at any point prior to PNCA or COI discontinuation, subsequently required vasopressors, a high frequency oscillating ventilator, or benzodiazepines, acetaminophen or anti-inflammatory agents as adjuncts for pain were discontinued early from the study. At the time of the study, acetaminophen was not used as routinely as it is now. In order to not confound pain assessment and opioid consumption by having some patients receive it and others not, the study team chose to stop data collection if acetaminophen (or benzodiazepine) was administered. Data collection terminated for all other patients when the PNCA or COI was discontinued. However, patient orders were monitored for 5 additional days to assess whether methadone was started.

Independent variables were collected to describe the sample and to determine whether groups were equivalent on all potentially confounding variables. Demographic and anthropometric data were extracted from the electronic health record, and included gender, race, ethnicity, gestational age, weight at time of surgery, total time PNCA or COI was used, and whether the current surgery was the infant's first. We also recorded mechanical ventilation and

any unplanned re-intubation occurrences. PNCA injections and attempts, as well as COI boluses were recorded for day (0700-1859) and nighttime (1900 – 0659) shifts. Mothers were asked about perinatal use of antidepressant or illicit drugs.

Primary Outcome

Our primary outcome was opioid consumption, defined as the average amount of opioid consumed over the time on study, and reported in mg/kg/hr. For the PNCA group, it was calculated based on the number of hourly injections plus the basal rate. For the COI group, it was based on the infusion rate across the time on study and any boluses administered.

Secondary Outcomes

- 1) Average pain intensity over the time on study. Participant pain intensity was assessed using the Revised-Face, Legs, Activity, Cry, Consolability (Revised-FLACC) scale (Malviya, Voepel-Lewis, Burke, Merkel, & Tait, 2006), the scale currently used in our NICU for this patient population. The FLACC has been used previously for NICU infants (Ahn, Kang, & Shin, 2005), has been validated in numerous pediatric populations (McGrath et al., 2008), and was originally validated in children from 2 months – 7 years (Merkel, Voepel-Lewis, Shayevitz, & Malviya, 1997).
- 2) Adverse events, defined a priori as naloxone rescue doses and any reintubation while on the opioid delivery system. Requiring methadone after the opioid delivery system was discontinued, was used as a measure of opioid tolerance. A modified Ramsey scale was used (Hoffman et al., 2002). Nurses reported sedation scores from 1 to 6, with 1 to 3 indicating significant sedation, 4 indicating asleep and easily arouseable or awake but drowsy, 5 indicating normal awake/alert, and 6 indicating anxiety and/or pain higher than baseline. Sedation scores below 4 were considered an indication of somnolence.

3) Parent and nurse satisfaction. No satisfaction tools in the extant literature would meet study requirements, therefore the investigators developed parent (Appendix A) and nurse (Appendix B) satisfaction surveys based on our previous studies (Czarnecki et al., 2017). Parents were asked about their satisfaction with 1) the pain management for their infant and 2) their involvement in the pain management for their infant. Parents in the PNCA group were also asked how often they pushed the PNCA button. Nurses were asked about 1) their satisfaction with the method of pain management for their patient, 2) whether parents were present during their shift, 3) whether they provided education to parents, and if so, 4) how long it took to provide the education. Directions for both surveys were explained at the time of consent to parents, and to nurses during daily rounds. Additionally, the study team contacted nurses on “off shifts” by phone to remind them of the need to complete the surveys. Printed blank copies of the parent surveys were left in their infant’s NICU suite. Printed blank copies of the nurses survey were available in a 2-sided envelope in the participant’s suite, with one side used to hold blank copies, and the other side clearly labeled for completed surveys (to protect anonymity). Parents were asked to complete the survey once a day, and nurses, once each shift. The research coordinator collected completed surveys daily.

Statistical Analysis and Data Management

Data were entered into a REDCap (<http://www.project-redcap.org>) database. Bimonthly reports were generated to look for missing data, outliers, and inconsistencies. Inconsistencies were checked against original data forms and corrections made as needed. CONSORT principles (Schulz, Altman, Moher, & Group, 2011) were used to assess recruitment success.

Statistical analyses were calculated using SPSS 24 (IBM SPSS Inc., Chicago, IL) and SAS 9.4 software (SAS Institute Inc.). An unadjusted two-sided $P < .05$ was used for statistical

significance in all analyses. Unless otherwise noted, all analyses include data from post-operative days (POD) 0-3. All participants who received the allocated intervention, and had at least one post-randomized outcome were included in the modified intent-to-treat analyses. In addition, descriptive and frequency analyses were used to provide summary information about patient characteristics. We report the median (Mdn) with Interquartile range (IQR) throughout. A Wilcoxon signed rank test was used to compare paired data of day and nighttime injections and attempts for the PNCA group, and paired day and nighttime boluses for the COI group. A Mann Whitney test was used to compare PCNA and COI groups; comparisons based on categorical data were analyzed using Chi-square or Fischer's exact tests. We used a mixed model with random post-operative day (POD) to examine the associations between opioid consumption and considered covariates, which included race, gender, surgery location, gestational age, study group and POD. Covariance structure used was AR(1), model was estimated by using maximum likelihood, POD and intercept were modelled as random effects. To meet the normality assumption of the linear mixed model, the outcome opioid consumption was transformed by using logarithm at base 10. For model selection procedure, we first included one of the considered covariates in the model to examine any time-varying effects on the outcome (univariable model analysis), then repeated the same procedure for other covariates. Based on the univariable model analyses, any covariates and interaction terms with $P < 0.20$ were included in the final multivariable analysis. The final model only includes those covariates with $P < 0.05$. Adverse events are reported based on incidence collapsed across POD.

Sample Size/Power Analysis

Based on our retrospective study (Czarnecki et al., 2014), and using an estimate of a large effect size, we planned to include 30 patients in each group (60 patients total). This sample size

would have allowed for an 80% power at 5% significance level to use a t-test to detect opioid consumption differences between groups of at least 0.74 SD. The study was terminated early however, due to difficulty recruiting, time and cost constraints.

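### The upper age limit was lifted during the trial, but the only age covariate in the opioid-consumption model is gestational age, so age at surgery goes unadjusted

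*Combined protocol and SAP*

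**What the plan says.** **Eligibility (Procedure, inclusion criteria).** Infants had to be born at 34 weeks or later, "having a corrected age no greater than 44 weeks at the time of enrollment". Because recruitment was difficult, "the protocol was amended to remove the upper age limit"; infants still had to be under NICU care.

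**Randomisation (Design).** "Randomization was stratified by gender and surgical location (thoracic, upper or lower abdomen) in blocks of 4". Age is not a stratification factor.

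**Baseline data (Protocol Details).** The variables taken from the health record include "gender, race, ethnicity, gestational age, weight at time of surgery, total time PNCA or COI was used". Neither postnatal nor corrected age at surgery is named, though the list is introduced as what was included and may not be exhaustive.

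**Analysis (Statistical Analysis and Data Management).** "A Mann Whitney test was used to compare PCNA and COI groups", without covariates. Opioid consumption on a log10 scale is also modelled by a linear mixed model with random intercept and random post-operative day. The covariates considered are "race, gender, surgery location, gestational age, study group and POD". A term enters the multivariable model if its univariable P is below 0.20 and stays only if P is below 0.05.

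**The concern.** Two infants born at the same gestational age can be operated on at different postnatal ages. The original cap bounded that difference: an infant born at 38 weeks could be at most 44 − 38 = 6 weeks old at enrolment, and one born at 34 weeks at most 10. After the amendment no numerical bound remains, only the condition of being in the NICU. The model then sees the same gestational age for infants who may differ considerably in age at surgery.

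No other listed element attributes that variation to age:

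- The mg/kg/hr outcome scales for weight, not for any age-related difference in consumption per kilogram.
- The random intercept leaves between-infant age effects in the unexplained variance.
- Weight at surgery, a partial proxy for age, is collected but is not a considered covariate.

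At stake is the precision of the adjusted group comparison, in a trial that was planned small and then stopped early. An age difference between arms that arose by chance could also shift the estimate without the model correcting for it.

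**Working it through.** **Inputs from the documents.** Two-sided alpha 0.05, 30 per arm, difference 0.74 SD, t-test, 80% power (Sample Size/Power Analysis; Statistical Analysis and Data Management).

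**Input assumed.** R², the share of outcome variance explained by age at surgery beyond the other covariates. The documents give no value, so 0% to 30% is shown.

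**Step 1: reproduce the stated power.** Noncentrality = d / √(2/n) = 0.74 / √(2/30) = 0.74 / 0.258 = 2.866. With 58 df the critical t is 2.002 and power is 80.5%. The difference detectable at 80% power is 0.736 SD. Both agree with the plan, and the point does not dispute its sample-size figure.

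**Step 2: add age at surgery.** Adjustment multiplies the residual SD by √(1 − R²) and costs one df (57 left). Noncentrality becomes 0.74 / [√(1 − R²) × 0.258].

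| Assumed R² | √(1 − R²) | Noncentrality | Power | Detectable at 80% |
|---|---|---|---|---|
| Unadjusted | 1 | 2.866 | 80.5% | 0.736 SD |
| 0% | 1 | 2.866 | 80.4% | – |
| 5% | 0.975 | 2.940 | 82.4% | 0.717 SD |
| 10% | 0.949 | 3.021 | 84.4% | 0.698 SD |
| 20% | 0.894 | 3.204 | 88.3% | 0.658 SD |
| 30% | 0.837 | 3.426 | 92.0% | 0.616 SD |

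Confidence-interval width falls by about 1 − √(1 − R²): 3%, 5%, 11% and 16% for R² of 5% to 30%. If age explains nothing, power moves only from 80.46% to 80.44%.

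**Step 3: a smaller trial.** The trial stopped early and the achieved size is not given. At an assumed 20 per arm, power is 62.6% unadjusted and 64.7%, 67.1%, 72.2% or 77.7% for R² of 5%, 10%, 20% or 30%.

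**Step 4: the other direction.** Suppose the 0.74 SD was set for the narrower population and the wider age range adds an assumed 10%, 25% or 50% to the variance. With age unmodelled, the standardised difference is 0.74 / √1.10 = 0.706, 0.74 / √1.25 = 0.662 or 0.74 / √1.50 = 0.604. Power at 30 per arm is then 76.6%, 71.3% or 63.4%.

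**Step 5: chance imbalance.** With age unstratified, the difference in mean age between arms has a standard deviation of √(2/30) = 0.26 SD of age at 30 per arm, and √(2/20) = 0.32 at 20. This is the same loss seen in a single realised sample, not an additional one.

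**Limit of the calculation.** Steps 1 to 4 treat one mean per infant with a t-test or ANCOVA. The plan uses a Mann-Whitney test and a repeated-measures model on the log10 scale, so the figures are a guide to scale and not the power of either analysis.

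**The case against.** The best case for leaving the plan alone has four parts.

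- **The gain may be nil.** The outcome is per kilogram, ordered background rates are weight-based, and both arms share a ceiling of 0.060 mg/kg/hr. All of this limits how far age alone could move consumption. The NICU requirement may have kept most infants young, and the documents give neither the age distribution nor the number enrolled under the amended rule. This stands: the size is unknown and every R² above is an assumption.
- **Randomisation already suffices.** It does for validity. A reader might infer that omitting age biases the group comparison; nothing in the documents supports that. The argument is about precision and chance imbalance only.
- **The data may not be to hand.** A reader might assume corrected age is known for every infant because eligibility depended on it. The amendment removed that dependence, and age at surgery is not among the listed variables. It should still be obtainable from gestational age with birth and surgery dates in the health record, but the documents do not say so.
- **Gestational age is undefined.** If it meant age at surgery, the gap would largely close. Age at birth is the normal meaning, but the plan should say which is intended.

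A reader might also infer that the covariate list was left unrevised when eligibility changed. The documents show one list and do not date it against the amendment, so only the present mismatch can be stated.

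**Conclusion.** The point holds as a matter of precision. Eligibility no longer bounds age, and neither the stratification nor the considered covariates include age at surgery. On the illustrative calculation, around the planned design each 10% of variance explained by age is worth about 4 percentage points of power, and including a useless age term costs almost nothing. This rests on the assumed R², on gestational age meaning age at birth, and on the t-test/ANCOVA approximation.

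It would be tempting to read the table as power recovered for the trial's main group comparison. The documents do not support that. The Mann-Whitney test takes no covariates, so a new model term leaves it unchanged, and any gain belongs to the model-based estimate. Nor do the documents show that infants of widely differing ages were in fact enrolled, only that the rules came to permit it.

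**What to change.** 1. Derive corrected age at surgery for every infant: gestational age at birth in weeks plus (date of surgery − date of birth in days) / 7. Add it to the listed baseline variables.
2. Keep this term in the log10 opioid-consumption mixed model together with study group, both exempt from the P < 0.20 and P < 0.05 screens. Otherwise a prognostic term can be dropped in a small sample. Study group is itself on the screened list, so the age-adjusted group estimate could vanish with it.
3. State whether gestational age means age at birth or age at surgery.
4. Tabulate age at surgery by arm.
5. State that the Mann-Whitney comparison remains unadjusted.
6. The document describes data collection as completed between April 2013 and April 2015. If the term is added after outcomes are known, label that model a sensitivity analysis and do not call it prespecified.

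Cost: one degree of freedom and a small derivation from dates that the health record should contain. No change to enrolment or treatment is involved.

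### The modified ITT set drops randomised infants who did not receive the allocated system, after an open-label assignment apparently made before surgery

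*Combined protocol and SAP*

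**What the plan says.** Four statements in the combined protocol and SAP matter together.

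- **Blinding (Design):** "This study utilized an unblinded design".
- **Assignment (Design):** "Parents were approached prior to surgery. After informed consent was obtained, infants were randomized to 1 of 2 arms". The section does not say in so many words that assignment came before the operation. It also describes no check of eligibility between surgery and assignment.
- **Start of treatment (Protocol Details):** "The post-surgical opioid delivery system was initiated upon return to the NICU".
- **Analysis set (Statistical Analysis and Data Management):** "All participants who received the allocated intervention, and had at least one post-randomized outcome were included in the modified intent-to-treat analyses". The plan describes no analysis of all randomised infants and no sensitivity analysis on the choice of set.

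Two eligibility criteria under Procedure are forecasts. Infants must be "expected to require opioids for at least 24 hours after the surgical procedure based on the opinion of the surgeon", and the last exclusion reads "3) who were expected to be chemically paralyzed after surgery". The vasopressor exclusion carries no time point. Under Protocol Details, enrolled infants who later need vasopressors, the oscillating ventilator or adjunct drugs leave the study early. They are not declared ineligible in retrospect.

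**The concern.** If the operation lies between assignment and treatment, things can change in that interval. The procedure may be altered or cancelled, or the infant may return in a state that was not forecast. Whether the allocated system is then started is decided by staff who know the arm. The arms are also run by different teams: the pain service manages PNCA and neonatology manages COI. The reasons for not starting, and how often that happens, could therefore differ by arm.

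The analysis set makes starting the allocated system a condition of being counted. That is selection on an event after randomisation, and randomisation no longer protects the comparison of opioid consumption, pain or adverse events. Infants who fail to start, or who are switched, are unlikely to be a random sample of their arm. The Mann-Whitney comparison and the mixed model would carry the same selection.

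**Working it through.** **1. The plan's own figure.** The inputs, from Sample Size/Power Analysis, are a two-group t-test, 5% significance (two-sided under Statistical Analysis), 80% power, a difference of 0.74 SD and 30 per group. The noncentral t calculation gives n = 29.66, so 30 per arm. Power at 30 per arm is 80.5% and the detectable difference is 0.736 SD. The stated figure reproduces and is not in dispute. It serves here only as the yardstick.

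**2. Who the analysis rule removes.** Apply its two conditions to each kind of randomised infant:

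- Started the allocated system and stayed on it: kept.
- Started it, then left early for vasopressors, the oscillating ventilator or adjuncts: kept, provided one outcome was recorded.
- Given the other system: dropped, although consumption can be measured.
- Never started on either system: dropped. The primary outcome as defined cannot be calculated for this infant in any case.

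The exposure is therefore the third and fourth groups. An as-randomised analysis recovers the third. The fourth can only be reported, or prevented by later assignment.

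**3. How far an arm's mean could move.** The documents give no count of infants dropped, so the counts below are assumptions. Take consumption as normal in SD units, with a fraction p dropped from one arm only and all of them that arm's highest consumers. The mean of those who remain shifts down by φ(z)/(1 − p), where z is the 1 − p quantile.

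- 2 of 30: p = 0.067, z = 1.50, shift 0.14 SD; 0.14/0.74 = 19% of the target.
- 3 of 30: p = 0.10, z = 1.28, 0.1755/0.9 = 0.195 SD; 0.195/0.74 = 26%.
- 6 of 30: p = 0.20, z = 0.84, 0.280/0.8 = 0.35 SD; 0.35/0.74 = 47%.

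If the tendency to be dropped correlates ρ with consumption, multiply the shift by ρ:

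- ρ = 0.5: about 0.07, 0.10 and 0.175 SD.
- ρ = 0.3: 0.06 SD at 10% dropped and 0.10 SD at 20%, or about 8% and 14% of 0.74 SD.

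**4. Effect on the test.** In a simulation with no true difference, 30 per arm randomised and a t-test, the false-positive rate in the worst case is about 9%, 13% and 28% for 2, 3 and 6 infants dropped, against a nominal 5%. At ρ = 0.5 it is about 6%, 7% and 10%.

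**5. Loss of power without bias.** If 30 per arm are randomised and the same fraction is dropped from both arms at random, power at 0.74 SD is 78.4% at 5% dropped, 76.1% at 10% and 70.9% at 20%. This cost is secondary to the bias.

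**The case against.** A reader might infer that infants were randomised before their eligibility could be known. The documents do not support that. Opioid need and paralysis are written as expectations, which can be judged before surgery, and an infant for whom the forecast fails was still eligible. Later vasopressor need is met by early discontinuation, and such infants stay in the analysis if they started the allocated system and have one outcome. That objection stands. It does not cover an infant who never starts, or who is given the other system.

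A reader might also infer that infants were in fact excluded, crossed over or unbalanced between arms. Nothing in the documents shows this. Even assignment before surgery is an inference from two adjacent sentences, though it is the natural one.

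Two further inferences should be set aside. The first is that knowledge of the arm altered analgesia in theatre. The plan says only that PNCA orders came from the pain service or the anesthesiologist, with no order time and nothing on care during the operation. The second is that stratifying on the planned surgical location is a flaw. It is a baseline factor and a valid one.

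The size calculation is open to fair criticism. It puts all losses in one arm, assumes perfect selection of the highest consumers, and measures a shift in a normal mean, whereas the plan uses Mann-Whitney tests and log-transformed consumption in the mixed model. It is a bound, not an estimate.

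None of this answers the remaining point: the analysis set depends on an event that follows a known assignment, and no all-randomised analysis stands beside it.

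**Conclusion.** The concern holds as a point about the analysis set, made sharper by the timing of assignment. The rule permits infants to be dropped after an open-label assignment for reasons that may differ by arm. It does not follow that this occurred, or that eligibility was unknowable at randomisation.

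The possible distortion is 0.14 to 0.35 SD in the worst case, or 19% to 47% of the 0.74 SD target. It is about half that at a correlation of 0.5 and smaller still at 0.3. The range assumes 2 to 6 of 30 infants dropped from one arm only and a normal outcome. If no infant failed to start or crossed over, this condition removes nobody and the bias is zero. The trial stopped before its planned size. With fewer infants per arm, each one dropped weighs more.

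The change should be made. The rule can bias the randomised comparison, and the remedy is cheap.

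**What to change.** **Analysis, still possible now that data collection has ended.** Remove receipt of the allocated system as a condition for the primary analysis set. Analyse every randomised infant with available outcome data in the assigned arm, including any given the other system. Keep the current set as a sensitivity analysis. State when randomisation took place relative to surgery, and report non-starters and crossovers by arm with reasons. The cost is one rewritten sentence, one additional run of the analyses and a short table. The limits are that infants never started on either system still contribute no consumption value, and that outcome data for crossovers must have been collected.

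**Design option, for a protocol of this type.** Keep consent before surgery, but release the assignment at the end of surgery after re-checking the existing criteria. Infants who fail the re-check are then consented but not randomised. Treatment is not delayed, because the system starts only on return to the NICU, and no extra patients are needed. There are three costs:

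- Assignment must be obtainable outside working hours, whereas the plan has the clinical research coordinator make it.
- Teaching PNCA parents to use the button moves to after surgery.
- The next allocation must stay concealed from whoever does the re-check. With open-label treatment and fixed blocks of 4 it could sometimes be guessed, and the re-check would then become a route for selection.

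### One fixed block size of 4 in an unblinded single-centre trial, with no locked release described, would make about 20-29% of assignments foreseeable to anyone who knew it and tracked the strata

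*Combined protocol and SAP*

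**What the plan says.** The Design section sets out the allocation: "Randomization was stratified by gender and surgical location (thoracic, upper or lower abdomen) in blocks of 4". It also states "This study utilized an unblinded design", and on the order of events, "After informed consent was obtained, infants were randomized to 1 of 2 arms". On roles it says "The randomization scheme was created by a statistician on the research team" and then "The clinical research coordinator used the scheme to assign participants to groups". No other block size is mentioned. The text does not describe sealed envelopes, central allocation or a locked release step, and does not say who could see the list or who knew the block size.

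The Procedure section makes eligibility depend partly on judgement: the infant had to be "expected to require opioids for at least 24 hours after the surgical procedure based on the opinion of the surgeon". It says candidates came from the surgery schedule and a surgical team "work list that included any infant with a planned surgery".

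The Sample Size/Power Analysis section plans 60 infants (30 per group) to detect a difference of 0.74 SD. It reports early termination and gives no final number enrolled.

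**The concern.** In an unblinded trial the staff see past assignments. With 1:1 allocation and blocks of 4, each block holds two infants per arm, so the end of a block can be deduced from its beginning. At a single centre one person could follow every stratum.

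Randomising after consent prevents choosing once an assignment has been revealed. It does not prevent foresight from influencing whom to approach or whom to judge eligible. If infants expected to use more opioid were steered towards one arm and those expected to use less towards the other, the arms would differ before treatment. The Mann Whitney comparison of groups is unadjusted. The covariates considered for the mixed model (race, gender, surgery location, gestational age, study group, postoperative day) do not include expected opioid need, so adjustment might not remove such a difference.

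**Working it through.** **Inputs from the documents.** Block size 4; two arms, with 1:1 allocation inferred from 30 planned per group; 2 genders x 3 locations = 6 strata; planned N = 60; design difference 0.74 SD; two-sided 5% level; 80% power.

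**Assumptions.** The observer knows the block size and the history in each stratum. Infants fall into the six strata with equal probability. Final N is not given, so a range is shown. The shift d among steered infants is 0.1 to 0.25 SD.

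**The plan's own figure.** With 30 per arm and 0.74 SD, the noncentrality is 0.74 x sqrt(30/2) = 2.87 on 58 degrees of freedom. Power of the two-sided 5% t-test is 80.5%, so the stated 80% reproduces.

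**Within one block of 4** (six equally likely sequences):
- Certain: first and second never; third with probability 1/3 (when the first two match); fourth always. Share = (0 + 0 + 1/3 + 1)/4 = 33.3%.
- Best guess correct: 1/2, 2/3, 2/3 and 1. Mean = 2.833/4 = 70.8%.

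**Across strata, with incomplete last blocks.** A stratum of n infants yields (4/3) x floor(n/4) certain assignments, plus 1/3 if n leaves remainder 3. Averaging over n ~ Binomial(N, 1/6), multiplying by 6 and dividing by N gives:

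| N | Certain | Best guess correct |
|---|---|---|
| 15 (assumed) | 15.6% | 62.9% |
| 20 (assumed) | 20.4% | 65.1% |
| 30 (assumed) | 25.0% | 67.1% |
| 40 (assumed) | 27.1% | 68.0% |
| 50 (assumed) | 28.3% | 68.6% |
| 60 (planned) | 29.2% | 69.0% |

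Hand check: exactly 10 per stratum gives 2 x 4/3 = 2.667 each, and 6 x 2.667/60 = 26.7%, close to the average for N=60.

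**Sensitivity.** Unequal strata change little (20.6-22.1% at N=20; 29.1-29.2% at N=60). Reading location as thoracic versus abdomen gives four strata, with 25.1% at N=20 and 30.6% at N=60. These are expectations: over all ways of filling six strata the share can be 26.7-33.3% at N=60 and 13.3-33.3% at N=20.

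**Possible bias.** Suppose infants in foreseen slots are shifted by +d in one arm and -d in the other.
- Steering on certain assignments only: false difference = 2 x d x P(certain).
  - N=60: 2 x 0.1 x 0.292 = 0.058 SD; 2 x 0.25 x 0.292 = 0.146 SD. Divided by 0.74, these are 8% and 20%.
  - N=20: 2 x 0.1 x 0.204 = 0.041 SD; 2 x 0.25 x 0.204 = 0.102 SD, or 6% and 14%.
- Steering on every best guess: false difference = 2 x d x (2 x accuracy - 1). N=60: 2 x 0.1 x 0.38 = 0.076 SD; 2 x 0.25 x 0.38 = 0.190 SD.

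**Random blocks of 4 and 6 at N=60**, with the observer knowing the possible sizes: certain 6.0%, best guess correct 67.2%. Bias from certain assignments falls to 2 x 0.1 x 0.060 = 0.012 SD and 2 x 0.25 x 0.060 = 0.030 SD. Bias from best guesses falls only to 0.069 and 0.172 SD.

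**The case against.** The strongest objection is that a chain of conditions must all hold. One person would need to know the block size, track six strata, influence approach or eligibility, forecast hourly opioid use, and want to steer. The documents establish none of these for any one person. They describe different roles for judging opioid need (surgeon), making the list (statistician) and assigning (coordinator). Candidates came from a broad list, and randomisation followed consent. This stands: the text supports a vulnerability, not an occurrence.

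Several stronger readings are tempting, but the documents do not support them.

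- **That concealment was absent or selection bias occurred.** Silence about release does not show either.
- **That the surgeon's criterion is nearly the primary outcome.** It is a yes/no opinion on whether opioids will be needed for at least 24 hours. The outcome is an average rate in mg/kg/hr. They are related, but an infant who needs opioids for longer need not use more per hour.
- **That the bias could plausibly reach 39% of the design difference.** That takes d = 0.5, a gap of 1.0 SD between infants steered in opposite directions. If steering means turning away the least suitable candidates (normal truncation), d = 0.5 requires declining 30% of candidates for foreseen slots with perfect forecasting, and 62% if forecast and actual use correlate at 0.5. For d = 0.25 the figures are 13% and 30%. The Procedure section says "As recruitment proved more difficult than anticipated" and that the upper age limit was removed, so refusals on the larger scale are unlikely.
- **That 29% describes the trial as run.** It belongs to the planned 60, and the trial stopped early.
- **That varying the blocks would be enough.** Best-guess accuracy hardly moves. If the coordinator held an open list, that role's foresight could be complete at any block size.

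Small fixed blocks do have a purpose: they keep balance in six sparse strata, about 10 infants each at the planned size.

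**Conclusion.** The point holds as an avoidable weakness of design. Given knowledge of the block size and tracking of each stratum, the expected share of certain assignments is 29% at the planned N of 60, about 20% at an assumed N of 20 and 16% at 15. Best guesses are right 65-69% of the time for N from 20 to 60, against 50% by chance.

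Under assumed shifts of 0.1 to 0.25 SD, steering on certain assignments would produce a false difference of about 0.06-0.15 SD at N=60, or 0.04-0.10 SD at N=20, compared with 0.74 SD. This sizes what is possible and does not estimate what happened. The documents give no SD in mg/kg/hr, so it cannot be put in the outcome's units.

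The result rests on six equally likely strata, an assumed final N and an assumed d. The arithmetic is firm; whether anyone had the foresight is unknown.

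**What to change.** At design, two changes together:

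1. Have the statistician or a locked system release each arm only after consent, eligibility and stratum have been recorded. This is the main protection, because it also covers whoever performs the assignment.
2. Generate the list with randomly varied, undisclosed blocks of 4 and 6. Even if the possible sizes became known, certain predictions at N=60 fall from 29% to about 6%. Best guesses fall only from 69% to 67%, which is why the first change is needed as well. A mix of 2 and 4 should be avoided, since best guesses at N=60 would then be right 70.6% of the time, slightly more often than with fixed blocks of 4.

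The cost is a different list and a release step, with no extra infants. Balance loosens slightly: the largest possible within-stratum difference rises from 2 to 3 infants. In simulated lists at N=60 the mean overall arm difference rises from about 1.7 to 1.9 infants, with the 95th percentile at 4 for both schemes.

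Recruitment is over, so what remains is a few sentences in the report. If assignments were not concealed, it should list fixed blocks of 4 in an unblinded trial as a limitation. Saying who held the list and whether the block size was hidden would let readers judge this.
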